7. DATA SOURCES

We will use the nationwide HIRA database of South Korea between 1 Mar 2012 and 31 Dec 2019 to identify all variables (exposure, outcome, covariates) needed to conduct this study. The HIRA database includes healthcare utilization information of residents of South Korea, with patient identifiers anonymized. Information on age, sex, diagnosis (ICD-10 diagnostic code, date of diagnosis, setting of diagnosis [inpatient, outpatient, emergency department], and others), medications dispensed/prescribed (national drug chemical code based on the active ingredient, date of prescription, days' supply, dose, route of administration, and others). Previous validation study that compared diagnosis codes recorded in the HIRA to those of recorded in electronic medical records found an overall positive predictive value (PPV) of 82.3%.

[figure not shown]

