a. Baseline conditions included: Charlson comorbidity index, HAS-BLED scores, comorbidities (antiphospholipid syndrome, asthma, cancer, chronic obstructive pulmonary disease, chronic kidney disease, chronic liver disease, diabetes mellitus, fracture, heart failure, hyperlipidemia, hypertension, ischemic heart disease, myocardial infarction, stroke, trauma), previous use of medications (corticosteroids, nonsteroidal anti-inflammatory drugs, angiotensin-converting enzyme inhibitors, angiotensin II receptor blockers, antiplatelet agents, azole antifungal agents, β-blockers, calcium-channel blockers, selective serotonin reuptake inhibitors, proton pump inhibitors, diuretics, thiazides, vasodilators, estrogens, cyclooxygenase-2 inhibitors), initial presentation of VTE (DVT, PE, both DVT and PE), number of outpatient visits

b. Earliest of: outcome of interest (major bleeding event), treatment discontinuation, switch to another anticoagulant, in-hospital death, end of the study period (31 Dec 2019)

Note: Dx, diagnosis; NOAC, non-vitamin K antagonist oral anticoagulant; Rx, prescription; VTE, venous thromboembolism; PE, pulmonary embolism

Figure 2. Overall study schematic

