8.3. Setting

8.3.1. Inclusion criteria

Patients must meet all of the following inclusion criteria to be eligible for inclusion in the study:

1. Incident VTE diagnosis in an inpatient or outpatient setting (International Classification of Diseases 10th Revision [ICD-10]: I26.0, I26.9, I80.2, I80.3) between 1 Mar 2013 and 30 Jun 2019
2. Received anticoagulation therapy (all medication codes for anticoagulants approved for VTE in Korea; unfractionated heparin [UFH], low molecular weight heparin [LMWH], warfarin, and NOACs) within 30 days of their VTE diagnosis (the index date will be defined as the date of treatment initiation with anticoagulants)
3. Aged ≥ 18 years at index date

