8.3.2. Exclusion criteria

Patients meeting any of the following criteria will not be included in the study:

1. Had a record of VTE diagnosis (ICD-10: I26.0, I26.9, I80.2, I80.3) within the 12-month period prior to the index VTE encounter.
2. Diagnosed with atrial fibrillation/flutter (ICD-10: I48), mechanical heart valve replacement (National Procedure Code: Z952, M6531, M6532, M6533, O1781, O1782, O1783, O1791, O1792, O1793, O1797, O1794, O1795, O1796, O1798, O1799) or mitral stenosis (ICD-10: I05.0, I05.2) anytime prior to index date.
3. Had a record of Inferior Vena Cava filter (National Procedure Code: O2045, M6650) anytime prior to index date.
4. Received anticoagulatory therapy within the 12-month period prior to index VTE encounter to restrict to new users of anticoagulatory therapy.
5. Prescribed two different anticoagulants on the same index date to prevent exposure misclassification.
6. Had a record of pregnancy (ICD-10: O03-O07, O10-O14, O16, O20-O026, O28-O36, O41-O43, O46.8, O46.9, O61-O66, O67.8, O67.9, O69, O70-O75, O80-O92, O94-O99, P08, Z33-Z39) within the 9-month period prior to index date.

7. Had a record of active cancer, defined as first diagnosis of cancer (ICD-10: C00-C97 [excluding non-melanoma skin cancer: C44]) with V code (V011, V027, V193, V194; a special code applied to patients with confirmed diagnosis of cancer by Korean Ministry of Health and Welfare for reimbursement for 5 years or longer if recurrent/metastasis) within the past 6 months of period prior to index date; or receiving anti-cancer treatment (chemotherapy, radiation therapy, or cancer related-surgery) under cancer diagnosis with V code within the past 6 months from index date (for Phase II of the study only). WHO-ATC codes and National Procedure Codes for anti-cancer treatment are shown in below table.

Anti-cancer treatment	WHO-ATC codes / National Procedure Codes
Chemotherapy	L01-04, H02AB02, H02AB04, H02AB06, H02AB07, H02AB09
Radiation therapy	HD051-HD059, HD061, HD071-HD073, HD080-HD089, HD091-HD093, HD110-HD115, HD121, HD150, HD160, HD211, HD212, HZ271

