*Blood transfusion (Korean Procedure Codes: X1001, X1002, X2011, X2012, X2021, X2022, X2031, X2032, X2041, X2042, X2051, X2052, X2061, X2062, X2071, X2072, X2081, X2082, X2091, X2092, X2101, X2102, X2111, X2112, X2121, X2122, X2131, X2132, X2141, X2142, X3010) will also be used to define other site bleeding history.

- Initial presentation of VTE
 - DVT (I80.2, I80.3)

- PE (I26.0, I26.9)
- Both DVT and PE
- Comorbidities (ICD-10 diagnostic code) will be measured within the 6-month period prior to the index date.
 - Antiphospholipid syndrome (D68.6, I82.9): As diagnosis of antiphospholipid syndrome is usually made after VTE diagnosis with subsequent diagnostic procedures, its presence will be evaluated within the 6-month period after the index date.
 - Asthma (J45)
 - Cancer (C00-C97): History of cancer (non-active) will be evaluated within a lifetime prior to the index date.
 - Chronic obstructive pulmonary disease (COPD; J40-J44)
 - Chronic kidney disease (N18, N19)
 - Chronic liver disease (B18, B19, K70-K77)
 - Diabetes mellitus (E10-E14)
 - Fracture (S22, S32, S42, S52, S62, S72, S82, S92, T10, T12)
 - Heart failure (I50)
 - Hyperlipidemia (E78)
 - Hypertension (I10-I15)
 - Ischemic heart disease (I24, I25)
 - Myocardial infarction (I21)
 - Stroke (I60-I64, I69, G45)
 - Trauma (T79, T98, V01–V99, W11–W17, W50–W52, W64, X34–X39, Y01–Y04, Y30–Y32)
- Previous use of medications (WHO-ATC code) will be measured within the 6-month period prior to the index date.
 - Corticosteroids (H02)
 - Nonsteroidal anti-inflammatory drugs (NSAIDs; M01A)
 - Angiotensin-converting enzyme (ACE) inhibitors (C09A, C09B)

- Angiotensin II receptor blockers (ARBs; C09C, C09D)
- Antiplatelet agents (aspirin [N02BA01], aspirin/dipyridamole [B01AC30], abciximab [B01AC13], beraprost [B01AC19], cilostazol [B01AC23], clopidogrel [B01AC04], iloprost [B01AC11], indobufen [B01AC10], limaprost [C04AX], ozagrel [R03DX], prasugrel [B01AC22], sarpogrelate [B01AC], ticagrelor [B01AC24], ticlopidine [B01AC05], tirofiban [B01AC17], treprostinal [B01AC21], triflusal [B01AC18])
- Azole antifungal agents (fluconazole [J02AC01], itraconazole [J02AC02], voriconazole [J02AC03], posaconazole [J02AC04])
- β -blockers (C07)
- Calcium-channel blockers (C08)
- Selective serotonin reuptake inhibitors (SSRIs; N06AB)
- Proton pump inhibitors (PPIs; A02BC)
- Diuretics (C03)
- Thiazides (C03A)
- Vasodilators (C01D, C04A)
- Estrogens (G03C)
- Cyclooxygenase (COX)-2 inhibitors (M01AH)

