- In the NOAC-based group, all analyses will be repeated stratified by each individual NOAC class (e.g, apixaban, dabigatran, rivaroxaban, edoxaban) to

PFIZER CONFIDENTIAL

identify the difference in baseline characteristics and treatment patterns between each NOAC class.

- To identify potential reasons for treatment change, clinical events preceding the first treatment change (major bleeding, thromboembolism diagnosis, complications of VTE, major surgery, active cancer, a new diagnosis of CKD or AKI, a new diagnosis of liver disease or abnormal liver function) will be measured within 30 days prior to the first date of treatment change. Patients can contribute with multiple events.
- All analyses of treatment patterns will be presented stratified according to the index anticoagulant treatment, and not overall or per drug class.

Phase II of the study (comparative)

Propensity score analysis

- To balance and adjust for any potential differences in baseline sociodemographic and clinical characteristics between treatment groups, propensity score (PS) methods will be implemented.
 - A logistic regression model will be used to estimate the predicted probability (propensity) of initiating each NOAC compared with warfarin given baseline covariates mentioned above. By using the estimated PS, we will apply the PS based on the inverse probability of treatment weights (IPTW), where the treatment group of interest will be given a weight of 1/PS, and the comparator group will be given a weight of 1/(1-PS) [4, 5]. The most extreme 1% of PS values (IPTW with trimming) will be excluded to improve comparability between exposure groups.

Main Analysis

- Sociodemographic and clinical characteristics will be summarized with means (STD) or median (IQR) for continuous variables and with count (proportions) for categorical variables for the two treatment comparisons of: apixaban vs warfarin, rivaroxaban vs warfarin, edoxaban vs warfarin and dabigatran vs warfarin (and NOAC vs NOAC, if scientifically feasible).
 - Differences in baseline covariates between users of different OACs will be assessed using the SD where the absolute SD <0.1 will be considered as well balanced.
- The incidence rate of major bleeding overall and by site will be presented as the total number of events per 1,000 person-years, with its 95% CIs estimated using the Poisson distribution.

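### The antiphospholipid syndrome variable includes I82.9, a code for thrombosis of an unspecified vein, so in an all-VTE cohort it can flag patients for the entry disease; the extent is unknown

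*SAP*

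**What the plan says.** The comorbidity list in SAP 8.4 gives two codes for the syndrome: "Antiphospholipid syndrome (D68.6, I82.9): As diagnosis of antiphospholipid syndrome is usually made after VTE diagnosis with subsequent diagnostic procedures". It then sets the window: "its presence will be evaluated within the 6-month period after the index date". Protocol 9.3 has the same two codes and the same window, so this is not a transcription slip in one document.

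The cohort consists entirely of VTE patients. SAP 8.3.1 requires "Incident VTE diagnosis in an inpatient or outpatient setting (International Classification of Diseases 10th Revision [ICD-10]: I26.0, I26.9, I80.2, I80.3"). The first exclusion in SAP 8.3.2 uses the same four codes: "Had a record of VTE diagnosis (ICD-10: I26.0, I26.9, I80.2, I80.3) within the 12-month period prior to the index VTE encounter". I82.9 appears in neither list.

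The variable is used in both phases. It is listed among the baseline conditions in the SAP 8.2 schematic ("Baseline conditions included: Charlson comorbidity index, HAS-BLED scores, comorbidities (antiphospholipid syndrome, asthma, cancer") and is a row in SAP Tables 1-4 and 13-16. It also falls under Potential Confounder(s), and SAP 10 uses a logistic model to "estimate the predicted probability (propensity) of initiating each NOAC compared with warfarin given baseline covariates mentioned above".

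The documents do not say why I82.9 is on the list, whether one code is enough, or how often either code occurs.

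**The concern.** D68.6 is the code that covers antiphospholipid syndrome. I82.9 is a residual venous-thrombosis code, close in the classification to I80.2 and I80.3, which the study itself uses for DVT. The plan justifies its late window by saying that the syndrome tends to be diagnosed after the clot. That explains a delayed D68.6, but it gives no reason to accept an unspecified-vein thrombosis as evidence of the syndrome.

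Every patient has just had a VTE and is being treated for it. A clinic that records the same clot less specifically at a later visit would turn that patient into a case.

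Two things are at stake. Describing clinical characteristics is a primary objective of Phase I, and this row could report VTE coding practice as if it were a comorbidity. In Phase II, a covariate meant to adjust for the syndrome would be measured with error of unknown size.

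**Working it through.** The plan states no figure for this variable, so there is none to reproduce. The check compares the code lists and then works through a range of assumptions.

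**Either code, or both?** Where the plan needs a combination, it writes it out. The major bleeding table in SAP 8.4 joins a diagnosis code to an admission code, plus brain imaging for intracranial events. The active-cancer exclusion in SAP 8.3.2 requires the cancer code together with a V code. The neighbouring comorbidities (fracture, diabetes, COPD and so on) are plain lists or ranges in which any code qualifies. The syndrome's list has that plain form, so a programmer would flag I82.9 alone.

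**Would another window cure it?** No. Before the index date, I82.9 could mark the work-up of the index clot or an earlier clot, since the prior-VTE exclusion does not list it. The use of a post-index window in a baseline propensity score is a separate matter.

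**Range.** Let p be the share of patients with the syndrome, all assumed to be captured. Let q be the share of the others who receive I82.9 in the window. Neither figure is in the documents; the values below are assumptions.

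- Reported prevalence = p + q(1 − p)
- False share of flagged patients = q(1 − p) / [p + q(1 − p)]

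For p = 1% and q = 5%: q(1 − p) = 0.05 × 0.99 = 0.0495; reported prevalence = 0.01 + 0.0495 = 0.0595; false share = 0.0495 / 0.0595 = 83%.

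| q | p = 1%: reported | p = 1%: false share | p = 5%: reported | p = 5%: false share |
|---|---|---|---|---|
| 0.5% | 1.5% | 33% | 5.5% | 9% |
| 1% | 2.0% | 50% | 6.0% | 16% |
| 5% | 6.0% | 83% | 9.8% | 49% |
| 20% | 20.8% | 95% | 24.0% | 79% |

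False flags outnumber true ones when q > p / (1 − p): 0.01 / 0.99 = 1.0% at p = 1%, and 0.05 / 0.95 = 5.3% at p = 5%.

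**The table row alone cannot reveal the error.** A reported prevalence of 5.95% arises from p = 1% with q = 5% (0.01 + 0.0495), where 83% of flags are false. It also arises from p = 5% with q = 1% (0.05 + 0.0095), where 16% are false.

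**Contrast between groups, again on assumed values.** With true prevalences of 1% and 2% and q = 5% in both groups, the reported values are 5.95% and 0.02 + 0.05 × 0.98 = 6.9%. A true ratio of 2 becomes 6.9 / 5.95 = 1.16. With p = 1% in both groups but q = 1% in one and 5% in the other, the reported values are 2.0% and 6.0%, a difference with no true counterpart.

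**The case against.** The strongest reply is that the size of the error is unsupported. Neither document gives a prevalence, an I82.9 frequency or a validity figure for these codes. If re-coding is rare, the variable is still serviceable: at p = 1% and q = 0.5%, about 67% of flagged patients are true cases. Nothing in the documents shows that clinics re-code I80 clots as I82.9, or that they do so more often under one drug than another. All of this stands. A reader might infer that the variable mostly counts the entry disease. That is true over part of the assumed range, not all of it, and the documents do not say where the study lies.

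SAP 7 does report that a validation study "found an overall positive predictive value (PPV) of 82.3"%. That does not settle the question: an I82.9 record can be a correct record of a venous clot and still be wrong as a record of the syndrome.

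The combination rule is also unstated, and requiring both codes would largely remove the problem. That is fair, but either code is the natural reading of the text, for the reasons given above.

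The meanings of D68.6 and I82.9 come from the ICD-10 classification, which the plan adopts, and not from its text. Some true cases may carry only I82.9, so deleting it is not free. Finally, this is one comorbidity among 15, alongside drug classes and risk scores, and Phase II is itself conditional on sufficient power. These points limit the weight of the concern without answering it.

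**Conclusion.** The concern holds in a limited form. As written, the rule can classify patients as having antiphospholipid syndrome because of the disease that brought them into the cohort, and no other part of the plan corrects this. Over the assumed range, the false share of flagged patients runs from about 9% (p = 5%, q = 0.5%) to about 95% (p = 1%, q = 20%). This rests on the standard meaning of I82.9, on an either-code reading, and on all true cases being captured.

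Two stronger conclusions might be drawn, and the documents support neither. One is that the propensity score would cease to adjust for the syndrome. D68.6 stays on the list, so patients with that code are still flagged; the adjustment is weakened to an unknown degree. The other is that the bleeding hazard ratios are biased. No such effect has been shown. Nor is I82.9 an entry code: the overlap is with the entry disease, not with the entry code list.

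The change is worth making before the tables are final and the propensity score is fitted. It does not threaten the study as a whole.

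**What to change.** In Protocol 9.3 and SAP 8.4, delete I82.9 and define antiphospholipid syndrome by D68.6 alone wherever the variable is used: SAP Tables 1-4 and 13-16, and the propensity score if the variable is kept there.

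Report, by treatment group and before fitting the propensity score, the number of patients with D68.6 only and with I82.9 only. The I82.9-only count is the number who leave the flag, and so the most true cases that the deletion could lose from it. It also shows whether use of the code differs between groups. If the sponsor prefers to keep I82.9, the plan should give the reason and state whether one code or both are required.

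The cost is one code removed in two documents and one short table of counts, with no new data. The downside is that any true cases coded only as I82.9 would be missed.

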8.2. Study population

The study cohort will be defined as patients diagnosed with VTE between 1 Mar 2013 and 30 Jun 2019. The cohort entry will be defined as the date of incident VTE diagnosis. The index date will be defined as the date of first prescription for anticoagulants within 30 days after the index VTE event. The length of the exclusion assessment window will vary depending on the condition, from 12-months at minimum to anytime prior to index date. The following patients will be excluded: A record of VTE diagnosis within the 12-month period prior to the index VTE encounter, diagnosed with atrial fibrillation, atrial flutter, mechanical heart valve replacement or mitral stenosis anytime prior to index date, had a record of Inferior Vena Cava filter anytime prior to index date, received anticoagulatory therapy within the 12-month period prior to index VTE encounter to restrict to new users of anticoagulatory therapy, prescribed two different anticoagulants on the same index date to prevent exposure misclassification, had a record of pregnancy within the 9-month period prior to index date, and for the Phase II of the study only, had a record of active cancer within six months period prior to index date.

Baseline sociodemographic characteristics (e.g., age, sex) will be assessed on the index date, whereas clinical characteristics (comorbidities, previous use of medications, Charlson comorbidity index [CCI], HAS-BLED scores, initial presentation of VTE, number of outpatient visits) will be assessed in the 6-month period prior to the index date except when otherwise specified in section 8.4 *Variables* (Figure 2).

Within this study cohort, we will describe the treatment patterns of anticoagulants prescribed for VTE treatment throughout the period of follow-up, defined as the period from the index date to the end of the study period. Moreover, if feasible, we will also examine the risk of major bleeding overall and by site, associated with each NOAC use, as compared with warfarin.

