Cancer surgeries	Specified in 'cancer-related surgery' of section 8.3.2
Benign surgeries	R4123-R4129, R4421, R4430, R3975
Cancer-related event (active cancer)	C00-C97 (excluding non-melanoma skin cancer, C44) with V code (V011, V027, V193, V194)
Kidney function change	
Chronic kidney disease	N18, N19
Acute kidney injury	N17
Liver function change	
Liver disease	B15-B19, K70-K77
Abnormal liver function	R94.5, R74.0

- **Phase II of the study**

- Major bleeding will be defined using primary or secondary diagnosis codes according to the ICD-10 diagnostic codes shown in below table and classified by site (intracranial, gastrointestinal [GI], all others).

Major bleeding	ICD-10 diagnosis code	Diagnostic definition
Intracranial hemorrhage	I60, I61, I62, I690, I691, I692, S064, S065, S066, S068	Diagnosis code + admission code + brain CT or MRI code

		* Brain CT or MRI: CT: HA441, HA451, HA461, HA471, HA851 MRI: HE101, HE102, HE135, HE201, HE202, HE235, HE301, HE302, HE401, HE402, HE501, HE502, HE535
GI bleeding	I850, I983, K2211, K226, K228, K250, K252, K254, K256, K260, K262, K264, K266, K270, K272, K274, K276, K280, K282, K284, K286, K290, K3181, K5521, K625, K920, K921, K922	Diagnosis code + admission code
Other bleeding	D62, H448, H3572, H356, H313, H210, H113, H052, H470, H431, I312, N020-N029, N421, N831, N857, N920, N923, N930, N938, N939, M250, R233, R040, R041, R042, R048, R049, T792, T810, N950, R310, R311, R318, R58, T455, Y442, D683	Diagnosis code + admission code

- The earliest date of diagnosis of the major bleeding event after the index date will be defined as the outcome occurrence date.
- Patients will be followed up from the index date to the occurrence of an outcome, treatment discontinuation (30-day grace period), switch to another anticoagulants, in-hospital death, or end of the study period (31 Dec 2019) whichever comes first.

Potential Confounder(s)

- Sociodemographic characteristics such as age, sex, and index year will be assessed at the index date.
- CCI [2] and HAS-BLED [3] scores will be measured within the 6-month period prior to the index date.

List of CCI	Score	ICD-10 codes
Cerebrovascular disease	1	G45, G46, H34, I60-I69
Congestive heart failure	1	I09.9, I11.0, I13.0, I13.2, I25.5, I42.0, I42.5-I42.9, I43, I50, P29.0
Chronic pulmonary disease	1	I27.8, I27.9, J40-J47, J60-J67, J68.4, J70.1, J70.3

Dementia	1	F00–F03, F05.1, G30, G31.1

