- The risk of major bleeding according to the treatment of interest will be investigated in time-to-event analyses using standard Kaplan-Meier methods.

- Cox proportional hazards model will be used to compare the safety outcome between users of different OACs, weighted on the estimated PS according to the IPTW approach.
 - Proportionality assumption will be tested by use of Schoenfeld residuals.

Subgroup Analysis

- The potential heterogeneity of treatment effects in selected subgroups of patients with VTE will be examined for the major bleeding as follows:
 - Aged <65 years vs. aged \geq 65 years
 - Females vs. males
 - Setting of VTE diagnosis (inpatient vs. outpatient)
 - Type of VTE (DVT without PE [ICD-10: I80.2, I80.3] vs. PE with or without DVT [I26.0, I26.9])
 - Major orthopedic surgery-provoked VTE
 - Major orthopedic surgery-provoked VTE is defined as an event preceded by knee arthroplasty, hip arthroplasty, or hip fracture surgery (National Procedure Codes: N0305, N0601, N0611, N0641, N0711, N2070, N0715, N2710, N0731, N0981, N0991, N1711, N3710, N1721, N3720, N1715, N4710, N1725, N4720, N2072, N2077, N2712, N2717, N3712, N3717, N3722, N3727, N4712, N4717, N4722 or N4727) within 3 months period prior to index date
 - With vs. without CKD stage 3 or 4 (N18.3, N18.4)
- P-for-interaction value <0.05 will be used to denote a significant difference between the two groups.

Sensitivity Analysis

- Vary the definition of treatment interruption/discontinuation to 15 and 60 days (allowing for varying non-adherence) to assess the effect this had on study outcomes.
- Four other approaches involving PS will be applied to determine the robustness of our study findings. First, we will vary the extreme value of PS in trimming process (most extreme 5%, and 10% will be excluded). Second, we will include the estimated PS, in addition to other covariates, into our multivariable Cox proportional hazards regression model. Third, we will stratify on the estimated PS in deciles. Last, we will apply another weighting approach, standardized mortality ratio weights, with the weights given as follows: 1 for the treatment group of interest and PS/(1 – PS) for the comparator group.[4]

- Exclude patients with a history of bleeding during the 6-month pre-index-date period in Phase II comparative analysis to evaluate the robustness of findings with respect to changes in underlying risk of patients

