Note: PAC, parenteral anticoagulants; IQR, Interquartile range; std, standard deviation

Table 13. Pre- and post-weighted baseline characteristics of patients with venous thromboembolism who newly initiated apixaban and warfarin.

Characteristics	Pre-weighted			Post-weighted		
	Apixaban		Warfarin-based therapy	Apixaban	Warfarin-based therapy	aSD
	N=	(%)	N=	(%)	N=	(%)
Follow-up (days; median, IQR)						
Age (years; mean±std)						
Age group (years; n, %)						
18-40						
40-65						
≥65						
Sex (n, %)						
Male						
Female						
Health insurance type (n, %)						
National health insurance						
Medical aid						
Index year (n, %)						
2012						
2013						
2014						
2015						
2016						
2017						
2018						
2019						
CCI score (mean±std)						
HAS-BLED score (mean±std)						
Comorbidities (n, %)						
Antiphospholipid syndrome						
Asthma						
History of cancer						
COPD						
Chronic kidney disease						
Chronic liver disease						
Diabetes mellitus						
Fracture						

Heart failure
Hyperlipidemia
Hypertension
Ischemic heart disease
Myocardial infarction
Stroke
Trauma
Previous use of
medications (n, %)
Corticosteroids
NSAIDs
ACE inhibitors
Angiotensin II receptor
blockers
Aspirin
 β -blockers
Calcium-channel
blockers
SSRI
Proton pump inhibitors
Diuretics
Thiazides
Vasodilators
Estrogens
Cyclooxygenase-2
inhibitors
Outpatient visits
(mean \pm std)

Note: ACE, angiotensin-converting enzyme; aSD, absolute standardized difference; CCI, Charlson comorbidity index; COPD, chronic obstructive pulmonary disease; IQR, interquartile range; NSAIDs, nonsteroidal anti-inflammatory drugs; PAC, parenteral anticoagulants; SSRI, selective serotonin reuptake inhibitors; std, standard deviation

Table 14. Pre- and post-weighted baseline characteristics of patients with venous thromboembolism who newly initiated rivaroxaban and warfarin.

Characteristics	Pre-weighted			Post-weighted		
	Rivaroxaban	Warfarin-based therapy	aSD	Rivaroxaban	Warfarin-based therapy	aSD
	N= (%)	N= (%)		N= (%)	N= (%)	
Follow-up (days; median, IQR)						
Age (years; mean±std)						
Age group (years; n, %)						
18-40						
40-65						
≥65						
Sex (n, %)						
Male						
Female						
Health insurance type (n, %)						
National health insurance						
Medical aid						
Index year (n, %)						
2012						
2013						
2014						
2015						
2016						
2017						
2018						
2019						
CCI score (mean±std)						
HAS-BLED score (mean±std)						
Comorbidities (n, %)						

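### Antiphospholipid syndrome is treated as a baseline confounder but measured in the 6 months after index; the propensity-score covariates are not listed, so the Phase II weights could use information from follow-up

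*SAP*

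**What the plan says.** - **Role of the variable.** Antiphospholipid syndrome appears under the potential confounders in Protocol 9.3 and SAP 8.4. Note (a) to Figure 2 (Protocol 9.1, SAP 8.2) counts it as baseline: "Baseline conditions included: Charlson comorbidity index, HAS-BLED scores, comorbidities (antiphospholipid syndrome, asthma, cancer".
- **Window.** For this variable, "its presence will be evaluated within the 6-month period after the index date". The stated reason is that the diagnosis is usually made after the VTE, once further tests are done. No other comorbidity has a post-index window.
- **General rule.** SAP 8.2 says clinical characteristics "will be assessed in the 6-month period prior to the index date except when otherwise specified in section 8.4". The exception changes the window. It does not take the variable out of the baseline set.
- **Protocol abstract.** The covariate paragraph puts comorbidities in the 6 months before index and makes no exception.
- **Propensity score.** SAP 10 and Protocol 9.7 model the "predicted probability (propensity) of initiating each NOAC compared with warfarin given baseline covariates mentioned above". Neither document lists these covariates or excludes any.
- **Follow-up for bleeding.** "Patients will be followed up from the index date to the occurrence of an outcome", so the antiphospholipid window and the risk period start together.
- **Checks.** Balance is judged by the rule that "the absolute SD <0.1 will be considered as well balanced". On robustness, "Four other approaches involving PS will be applied to determine the robustness of our study findings". There are also two alternative grace periods and an exclusion for prior bleeding.

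**The concern.** A propensity score models the choice of drug at the index date, so it should use only what was known by then. A code entered up to 6 months later can follow a bleed, a switch or a discontinuation, and nothing in the text stops the window at those events. A patient who dies in hospital after an early bleed also has no further time in which to be coded. The stated rationale explains why the window is late and is reasonable for Phase I description. It does not make the code a pre-treatment variable.

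If coding depends on both drug and bleeding, weighting on it can shift the primary hazard ratio for major bleeding. The planned analyses would not show this:

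- None of the sensitivity analyses drops or redefines the variable. They change trimming, adjustment, stratification, weighting, grace period or bleeding history.
- SAP Tables 1 and 3 would show whether coding differs by drug, but no planned output shows whether it depends on bleeding.
- The E-value analysis in Protocol 9.9 is specified only for apixaban and does not address post-index measurement.

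**Working it through.** **Reading the text.** The variable is in the confounder list and in the baseline note; the exception clause alters only its window; the propensity score takes the baseline covariates without exclusion. Together these make inclusion the most natural reading. No sentence states it.

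**Size.** The plan gives no figure on this point to reproduce and no coding frequency, so this is an illustration.

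Inputs from the study-size section (SAP 9, Protocol 9.5), as NOAC share *a* and bleeding probability *p*: apixaban 39.3%, 1.19%; rivaroxaban 69.1%, 8.1%; edoxaban 31.0%, 8.5%; dabigatran 16.8%, 1.4%.

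Assumed inputs: 1-2% of patients coded; coding 3-5 times likelier after a bleed early enough to matter; 2-3 times likelier on warfarin; a share *f* of bleeds early enough. The true ratio is 1.00.

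Formulas, with bleed multiplier *k* and drug multiplier *m*:
- Average multiplier among bleeders: g = 1 + f(k − 1).
- Base coding rate: b = P(C) / {[a + (1 − a)m] × [1 + p(g − 1)]}.
- Weighted risk in arm A: p × Σ over c of P(c) × P(c | A, bleed) / P(c | A).

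Upper apixaban case at f = 50% (2% coded, k = 5, m = 3):
- g = 3; b = 0.02 / (2.214 × 1.0238) = 0.00882.
- Coded among bleeders: apixaban 0.02647, warfarin 0.07941. Coded overall: apixaban 0.00903, warfarin 0.02710.
- Apixaban risk: 0.0119 × [0.02 × 0.02647/0.00903 + 0.98 × 0.97353/0.99097] = 0.01215.
- Warfarin risk: 0.0119 × [0.02 × 0.07941/0.02710 + 0.98 × 0.92059/0.97290] = 0.01173.
- Ratio: 1.036. The lower case (1%, k = 3, m = 2) gives 0.011944/0.011871 = 1.006.

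| Comparison | f = 100% | f = 50% | f = 25% |
|---|---|---|---|
| Apixaban | 1.012-1.071 | 1.006-1.036 | 1.003-1.018 |
| Rivaroxaban | 1.012-1.074 | 1.007-1.041 | 1.003-1.022 |
| Edoxaban | 1.009-1.047 | 1.005-1.027 | 1.003-1.014 |
| Dabigatran | 1.011-1.057 | 1.005-1.029 | 1.003-1.015 |

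If NOAC users are instead coded 2-3 times more often, apixaban becomes 0.956-0.993 at f = 50% and 0.916-0.986 at f = 100%. If either multiplier is 1, the ratio is 1.000.

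A separate set of assumptions (true prevalence 1%, bleeding risk 5%, detection 50% on warfarin and 20% on a NOAC, multiplied by 0.5 to 3 after a bleed) gives 0.999-1.006, and 0.985-1.061 at 10% prevalence. It agrees that the bias can go either way and is small if the condition is rare.

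**Balance check.** In the apixaban scenarios with warfarin users coded more often, the pre-weighting absolute standardised difference takes four values: 0.065 and 0.096 (1% coded, m = 2 and 3), 0.092 and 0.136 (2% coded). Three of the four fall below 0.1. After weighting the difference is near 0 whether or not bias exists, so the rule cannot settle the matter.

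**Cost of not adjusting.** For a true confounder with prevalence 1-2%, *m* times commoner on warfarin (2-3) and bleeding risk ratio *r* (1.5-3), all assumed: u = prevalence / [a + (1 − a)m] and ratio = [1 + u(r − 1)] / [1 + m·u(r − 1)]. Apixaban upper case: u = 0.02/2.214 = 0.00903, ratio = 1.01807/1.05420 = 0.966. Lower case: u = 0.01/1.607 = 0.00622, ratio = 1.00311/1.00622 = 0.997. Across the four comparisons the range is 0.954-0.997.

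**The case against.** **Use in the weights is inferred.** This stands. The Protocol abstract supports a pre-index reading, and its analysis paragraph speaks only of baseline characteristics. A reader might take the antiphospholipid row in SAP Tables 13-16 (Table 13: "Pre- and post-weighted baseline characteristics of patients with venous thromboembolism who newly initiated apixaban and warfarin") as proof that the post-index variable is in the score. It is not. Those tables also list follow-up time, which cannot be a covariate. They look like shells from before the amendment: they show aspirin instead of antiplatelets, have no antifungal row, and include index year 2012 although the cohort opens in March 2013. What remains is a conflict over the window and an unstated covariate set, and both need resolving whatever was intended.

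**The post-index code may be a useful proxy.** If the condition was present at index and only diagnosed later, the late code carries real confounder information. This also stands, and it limits the remedy. On the log scale the apixaban extremes are equal: ln 1.036 = 0.035 for the bias at f = 50%, and ln 0.966 = −0.035 for full non-adjustment. At f = 25% the bias is about half that (ln 1.018 = 0.018). Dropping the variable altogether is therefore not an equal alternative. Full non-adjustment is also the worst case for a pre-index definition, which still captures cases already coded.

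**No harm is shown from the documents.** Correct: every coding input is assumed, and Phase II is itself conditional on feasibility. The case for change rests on the timing principle, the unlisted covariates and the low cost.

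**Conclusion.** The concern holds as a timing defect with an inferred consequence. The documents state that a listed confounder is measured after index, that bleeding follow-up starts at index, and that the propensity score takes the baseline covariates without a list or an exclusion. They do not state that the variable enters the score.

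A reader might infer that the primary hazard ratio is biased, or biased against a particular drug. The documents do not support that. Bias needs coding to depend on both drug and bleeding, and nothing in them says whether either dependence holds. Under the assumed inputs with half of bleeds early, the effect is a few per cent at most for apixaban, in either direction, and it vanishes if only one dependence holds. It is worth fixing because the planned analyses would not reveal it and the fix is cheap, with medium confidence given the inference involved.

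**What to change.** 1. Itemise the propensity-score covariates for Phase II in SAP 10 and Protocol 9.7, each with its window.
2. For the Phase II propensity score, weights and Tables 13-16, define antiphospholipid syndrome from codes on or before the index date, with a stated look-back. Data start on 1 March 2012 and the cohort on 1 March 2013, so every patient has at least 12 months of history.
3. Keep the post-index definition for Phase I description, labelled as post-index, and run it as one Phase II sensitivity analysis so that both results are reported.
4. Reconcile the Protocol abstract with Protocol 9.3 and SAP 8.4, and bring the rows of Tables 13-16 into line with the current covariates.

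The cost is a short wording change in each document, a covariate list and one extra sensitivity run for the four comparisons. The downside should be stated in the limitations: by the plan's own rationale many cases are not yet coded at index and would stay unadjusted. Any difference between the two definitions should be reported as uncertainty and not read as showing which result is correct.
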